8.5 Modifications for Other Adverse Events

The patient will be removed from protocol treatment for any related Grade 4 non-hematologic toxicity or other dose-limiting toxicity as described.

- 8.5.1 Patients should receive appropriate medical management for adverse events. Treatments may be delayed for clinically significant Grade 2 or 3 adverse events and unrelated Grade 4 adverse events at the discretion of the treating physician. If treatment cycles are delayed for more than 4 weeks due to adverse events, the patient will be removed from protocol treatment.
- 8.5.2 Management of nivolumab-related adverse events should be per standard of care.

9.0 CONCOMITANT THERAPY

Medications used during the course of the study should be documented.

9.1 Prohibited Concomitant Therapy

- The administration of concurrent medications intended to treat the primary cancer is not allowed during protocol therapy. This includes any chemotherapy, investigational agent, biologic agent or other anti-tumor agents. Radiation therapy is also prohibited, however, patients who have not achieved a PR by the mid-course imaging AND have > 1 site of measurable disease may receive low dose (up to 4Gy) radiation to a solitary site at the discretion of the treating investigator. Responding radiated sites will not be included in response assessments.
- Topical and inhaled corticosteroids to treat other medical conditions are allowed. Systemic corticosteroids up to the equivalent of 20 mg prednisone per day are allowed. Intermittent corticosteroid usage to treat infusion reactions is allowed.

- 9.2 Patients should be strongly discouraged from taking any “alternative” or “naturopathic” medications since these agents may interact with BV. Any use of these medications should be at the judgment of the treating physician and should be documented in the patient’s medical record.

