1.0 OBJECTIVES

1.1 Primary objectives

1.1.1. ARM A:

To estimate the response rate following weekly brentuximab vedotin (1.2mg/kg 3 of 4 weeks for up to four 28-day cycles) in patients with lack of response (<PR) or progression following brentuximab vedotin and demonstrating persistent expression of CD30.

1.1.2 ARM B:

To evaluate the response rate of combination brentuximab vedotin and nivolumab in patients with lack of response (<PR) or progression within 6 months following brentuximab vedotin

1.2 Exploratory objectives (will be completed as feasible, based on availability of data collected in the course of standard clinical assessments/follow-up)

1.2.1. To monitor clinical outcome following the study treatment regimen.

1.2.2. To estimate the frequency of CD30 loss in patients following resistance to brentuximab vedotin.

1.2.3. To describe the pattern of CD30 expression (membranous, cytoplasmic, golgi) in comparison to the pre-brentuximab vedotin expression.

1.2.4. To semi-quantitatively estimate and compare the surface density of CD30 pre and post brentuximab vedotin as measured by flow cytometry.

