13.0 STATISTICAL CONSIDERATIONS

- 13.1 The primary objective of the trial is to determine the overall response rate as measured by the Cheson 2007 criteria. Since this a pilot study exploring both the feasibility and potential efficacy of this strategy likely in a range of histologies and clinical scenarios (e.g. primary refractory vs PD after prior response to brentuximab vedotin) no formal statistical measures will be pre-specified. However, we will deem this protocol a “success” if the absolute response rate in this group of patients is $\geq 20\%$ in Arm A or $\geq 40\%$ in Arm B. We expect to treat up to 20 patients on each arm in this study.
- 13.2 Anticipated accrual per Arm: We anticipate accrual of 20 patients over 18 - 24 months. As arm A is closed, we anticipate accruing 20 patients to Arm B.
- 13.3 Estimated distribution of study population by gender, ethnicity and race.

MAXIMUM ANTICIPATED ENROLLMENT in Arm B			
Ethnic Category	Sex / Gender		
	Females	Males	Total
Hispanic or Latino	0	1	1
Not Hispanic or Latino	8	11	19
Ethnic Category Total of All Subjects*	8	12	20
Racial Categories			
American Indian / Alaska Native	0	0	0
Asian	0	0	0
Native Hawaiian or Other Pacific Islander	0	0	0
Black or African American	0	1	1
White	8	11	19
Racial Categories: Total of All Subjects*	8	12	20

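### Section 9.1 lets patients below PR be irradiated mid-course, and no rule stops their post-radiation assessment from counting in the primary drug response rate

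*Combined protocol and SAP*

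**What the plan says.** The Arm B objective in section 1.1 concerns two drugs: "To evaluate the response rate of combination brentuximab vedotin and nivolumab in patients with lack of response". Radiation is not part of that regimen. Section 13.1 makes overall response rate the primary objective, measured by the 2007 revised lymphoma response criteria. It calls Arm B a success at 40% or more and expects up to 20 patients per arm. It also says that "no formal statistical measures will be pre-specified".

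Section 9.1 prohibits radiation during protocol therapy, with one exception: "patients who have not achieved a PR by the mid-course imaging AND have > 1 site of measurable disease may receive low dose" treatment of up to 4 Gy. It describes this as "radiation to a solitary site at the discretion of the treating investigator". The next sentence is "Responding radiated sites will not be included in response assessments".

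Under section 12, patients with stable disease after cycle 2 may continue. The study calendar in section 11 requires CT after cycle 2 and again after therapy. An irradiated patient who stays on protocol will therefore normally have a post-radiation scan.

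The plan does not say:
- whether that patient's response is fixed before radiation;
- what makes an irradiated site a responding one;
- whether a dropped site also leaves the baseline sum.

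No sensitivity analysis is described.

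**The concern.** The lesion set used for response can change after baseline. It changes only in patients who are below PR at mid-course, at a site picked with the scan in hand, and according to what the site does after radiation. The site chosen may well be the one holding the patient out of PR. Once it is gone, the remaining lesions decide the classification, and they may already have shrunk enough. The patient then enters the numerator of the drug response rate although the drugs did nothing more after the mid-course scan.

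At stake is the Arm B success call, which compares an observed proportion in about 20 patients with a fixed bar and has no formal test around it.

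**Working it through.** **Inputs from the plan.** Arm B has up to 20 patients and a bar of 40% (section 13.1). 0.40 × 20 = 8, so success means at least 8 responders. No alpha, power or null rate is given, so there is no other figure to reproduce.

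**Assumptions.** PR is a fall of at least 50% in summed lesion size (the criteria are cited but not reproduced). A dropped site leaves both the baseline and the follow-up sum. A site is responding if it has fallen by at least 50% from baseline. All lesion sizes are invented.

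**1. A conversion in one patient.**
- Baseline: 4 + 4 + 6 = 14.
- Mid-course: 2 + 2 + 6 = 10. The fall is (14 − 10)/14 = 28.6%, not PR, so radiation is allowed.
- The 6 is irradiated, responds and is dropped. The rest go from 8 to 4: (8 − 4)/8 = 50%, which is PR. No unirradiated lesion has changed since mid-course.

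**2. Is the dropping rule the cause?** Let w be the irradiated site's share of the baseline sum, s its fall and r the fall in the other sites. The total fall is ws + (1 − w)r.
- If s ≥ 50%, the site is dropped and PR requires r ≥ 50%. With both at or above 50%, the total is also at least 50%, so keeping the site would give PR too. In the example, the 6 falls to 3 or less and 14 goes to at most 7, again at least 50%.
- If s < 50%, the site is kept. A total of at least 50% then requires r > 50%, so dropping every irradiated site would also give PR.

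Under these assumptions the rule is at least as strict as either alternative. If response were judged against the size just before radiation, this guarantee would not follow, and section 9.1 does not say which applies.

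**3. The reverse case.** From the same baseline, suppose the drugs alone would have given 2.5 + 2.5 + 2 = 7, a 50% fall and so PR. If the 6 is irradiated, responds and is dropped, the rest go from 8 to 5, a fall of 3/8 = 37.5%. That drug response is lost.

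**4. Net direction.** A two-site simulation used assumed inputs: mean mid-course shrinkage 25% (SD 30 points), mean further drug change 5 points (SD 15), radiation response in 80%, and between-site correlation 0 to 0.9. Among irradiated patients below PR, drug-only response was 10.6% to 11.3%. Under the plan's rule it was 16.9% to 32.5% when the worse site was irradiated and 12.5% to 18.6% when the site was random. Upward moves outnumbered downward ones in every scenario.

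**5. Effect on the verdict.** One patient is 1/20 = 5 points. If one of 8 counted responders is a conversion, the drug result is 7/20 = 35%, below the bar. If two are, it is 6/20 = 30%.

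**6. Illustration of scale.** Let p be the true drug response rate and c the share of non-responders converted. The observed rate is p + (1 − p)c. With p = 30%, 20 × 0.70 = 14 non-responders are expected. The exact binomial P(at least 8 of 20) is:
- c = 0: rate 30.0%, P = 22.8%
- c = 5% (0.7 patients expected): rate 33.5%, P = 34.4%
- c = 10% (1.4 patients): rate 37.0%, P = 47.3%
- c = 15% (2.1 patients): rate 40.5%, P = 60.2%

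With p = 20%, c = 5% raises P from 3.2% to 8.3%. Neither p nor c comes from the documents.

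**The case against.** The strongest reply is that the quoted sentence is a safeguard: it stops radiation shrinkage from being credited to the drugs. That stands. A reader might infer that dropping responding sites is the lenient choice and that the cure is to put them back. Step 2 shows otherwise when response is judged against baseline: keeping the post-radiation size would give at least as many responders.

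A reader might also infer that the rule can only turn non-responders into responders. Step 3 refutes that. Upward is the expected net direction, not a certainty for each patient.

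Conversion also needs a long chain. The patient must be below PR without progression, since progression ends protocol treatment (section 7.5), and must have more than one measurable site. The investigator must choose to irradiate, the site must respond, and the other lesions must reach PR. The documents give no frequency for any step, so the rates in step 6 only illustrate.

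Finally, this is a pilot with an informal benchmark, and 7/20 and 8/20 are hardly distinguishable (exact 95% intervals 15.4% to 59.2% and 19.1% to 63.9%). That lowers the severity. It does not remove the gap, because the plan sets its own bar on the observed rate and one patient can decide it.

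**Conclusion.** The point holds as a missing classification rule. The fault is that post-radiation assessments still feed the primary endpoint for patients irradiated before reaching PR, while the objective concerns the drugs alone. The exclusion of responding sites limits this only in part. The expected net bias is upward, 5 points per net conversion in 20 patients, and one conversion is enough to change 7/20 into 8/20.

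The total size is unknown, because use of radiation is not documented. The documents do not support a statement that the Arm B rate is in fact inflated, or by how much. The worked case rests on the assumed 50% definition of PR and on the dropped site leaving the baseline sum as well. This should be fixed, in proportion to a pilot.

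**What to change.** Add to sections 9.1 and 13.1: for the primary response rate, an irradiated patient's response is the one recorded at the last assessment before radiation, on the full baseline lesion set, so a patient irradiated before reaching PR counts as a non-responder. The patient in step 1 then stays at a 28.6% fall, not PR.

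Also report how many patients were irradiated. Give the response rate a second time as a sensitivity or exploratory result, using post-radiation response in unirradiated lesions with the irradiated site removed from both the baseline and the follow-up sum. Label it as the more generous reading: by step 2 it can only equal or exceed the rate under the current rule.

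The cost is a few sentences and no new data beyond the scans already required. The downside is that a genuine late drug response after radiation is not credited in the primary analysis, at 5 points each in 20 patients. A late response in the unirradiated lesions stays visible in the second analysis. Permission to irradiate is unchanged.

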10.0 CORRELATIVE STUDIES

- 10.1 Correlative studies will include a peripheral blood at baseline and Day 1 (+/- 2 days) of each cycle and up to 10 unstained slides of diagnostic tumor tissue, if available. These assays can include assessment for PD1/PDL1 expression, T-cell subsets, and cytokines and will be correlated with clinical endpoints in an exploratory, hypothesis-generating fashion.

11.0 STUDY CALENDAR

Required Studies	Pre-Entry (Within 4 weeks of enrollment unless indicated otherwise)	Within 3 Days Prior to Each Cycle	Post Cycle 2	Post Therapy ⁷	Follow-Up
Physical					
Medical history	X				
Physical exam	X	X ¹⁰		X ⁷	X ⁸

Performance status	X	X ¹⁰		X ⁷	
Clinical disease assessment	X	X ¹⁰		X ⁷	
Adverse event assessment	X	X ¹⁰		X ⁷	
Cardiology					
EKG	X				
Lab					
CBC with differential, platelets	X	X ¹⁰		X ⁷	
Serum creatinine, total bilirubin, SGOT (AST), electrolytes, glucose	X	X ¹⁰		X ⁷	
TSH	X			X	
Albumin (Hodgkin's lymphoma)	X ¹				
LDH	X ²			X ⁷	
Bone marrow studies	X ³			X ^{3,7}	
Pregnancy test	X ⁹				
Molecular studies	X ⁴			X ^{4,7}	
Correlative Studies	X ¹⁴	X ¹⁴			
Lymph node (tumor) biopsy to assess CD30 expression	X ¹¹				
PFT with DLCO	X ¹²				
Pregnancy test	X ¹³				
Radiology					
CT chest, abdomen and pelvis; CT neck if cervical adenopathy present	X		X ⁵	X ^{5,7}	
PET/CT	X ⁶			X ^{6,7}	

¹ Albumin is *recommended* in patients with Hodgkin's lymphoma for documenting staging/prognostic criteria

² LDH must be done within 14 days prior to study entry.

³ Bone Marrow Studies include aspirate and unilateral or bilateral biopsy, flow cytometry if clinically indicated. If all bone marrow studies are negative at enrollment, these do not need to be repeated at completion of the study. Baseline bone marrow may be waived with PI or Sub-Investigator's approval. Patients who do not have bone marrow studies done at baseline will need to have bone marrow studies at completion of treatment to confirm CR if needed.

⁴ Molecular Studies: May be done on blood or bone marrow at enrollment and at completion of the study at the discretion of the treating physician and availability of such testing. If these studies are negative at enrollment, they do not need to be repeated.

⁵ CT scans are required post cycle 2 and post therapy.

⁶ PET scans are strongly recommended pre-therapy and are required post therapy to confirm CR.

⁷ Post therapy studies should be done 3 - 5 weeks post cycle 4 or after the patient's last cycle, whichever comes first, unless clinically indicated.

⁸ Follow-up should be done as per the clinical standard of care. A typical schedule includes every 3 months for 1 year then every 6 months for 4 years (total follow-up time 5 years)

⁹ Pregnancy test in women of childbearing potential.

¹⁰ For Cycle 1 Day 1, pre-entry physical exam, performance status, disease assessment and adverse event assessment may be used (these do not need to be repeated within 3 days) and labs done within 14 days are acceptable.

¹¹ This requirement will be waived for patients who have had a previous lymph node biopsy (documenting CD30 expression or with tissue available for CD30 testing) performed at any time. Additional CD30 expression data from earlier or follow-up clinical records will be used as appropriate for comparison with study entry data.

¹² PFT with DLCO can be within 90 days.

¹³ Pregnancy test should be within 7 days of the first dose of study drug.

¹⁴See Section 10 Correlative Studies for additional information

12.0 CRITERIA FOR EVALUATION AND ENDPOINT DEFINITIONS

Definitions of Disease, Criteria for Evaluation and Endpoint Definitions. Response will be defined by standard NCI criteria (Cheson *et al*) for lymphoid malignancies [24].

The initial response assessment will occur after Cycle 2. After Cycle 2, patients with a complete response (CR), partial response (PR), or stable disease (SD) will be allowed to receive additional cycles of BV using the same schedule and dose adjustments as noted above. Patients who achieve clinical benefit at the discretion of the treating physician and have not experienced unacceptable toxicities may receive up to 4 cycles total on study. Disease assessments should be performed per standard of care, but in general every 2 - 3 cycles and at the conclusion of therapy. PET should be used to evaluate residual masses that were previously FDG-avid whenever possible.

13.0 STATISTICAL CONSIDERATIONS

- 13.1 The primary objective of the trial is to determine the overall response rate as measured by the Cheson 2007 criteria. Since this a pilot study exploring both the feasibility and potential efficacy of this strategy likely in a range of histologies and clinical scenarios (e.g. primary refractory vs PD after prior response to brentuximab vedotin) no formal statistical measures will be pre-specified. However, we will deem this protocol a “success” if the absolute response rate in this group of patients is $\geq 20\%$ in Arm A or $\geq 40\%$ in Arm B. We expect to treat up to 20 patients on each arm in this study.
- 13.2 Anticipated accrual per Arm: We anticipate accrual of 20 patients over 18 - 24 months. As arm A is closed, we anticipate accruing 20 patients to Arm B.
- 13.3 Estimated distribution of study population by gender, ethnicity and race.

MAXIMUM ANTICIPATED ENROLLMENT in Arm B			
Ethnic Category	Sex / Gender		
	Females	Males	Total
Hispanic or Latino	0	1	1
Not Hispanic or Latino	8	11	19
Ethnic Category Total of All Subjects*	8	12	20
Racial Categories			
American Indian / Alaska Native	0	0	0
Asian	0	0	0
Native Hawaiian or Other Pacific Islander	0	0	0
Black or African American	0	1	1
White	8	11	19
Racial Categories: Total of All Subjects*	8	12	20

14.0 GUIDELINES FOR ADVERSE EVENT MONITORING AND REPORTING

14.1 Definitions

Adverse Event (AE) is defined as any unfavorable and unintended sign (including an abnormal laboratory finding), symptom, or disease temporally associated with the use of a medical treatment or procedure.

Serious Adverse Event (SAE) is defined as an AE that results in any of the following outcomes:

- Death;
- A life-threatening AE (i.e., the patient/subject was, in the view of the initial reporter/investigator, at immediate risk of death from the AE as it occurred. It does not refer to an AE that hypothetically might have caused death if more severe);
- Inpatient hospitalization or prolongation of existing hospitalization (i.e., hospitalization was required to treat or diagnose the AE: excludes hospitalization for unrelated reasons);
- A persistent or significant disability or incapacity (disability here means that there is a substantial disruption of a person's ability to conduct normal life functions);
- A congenital anomaly/birth defect;
- An important medical event (i.e., AEs that might not be immediately life-threatening, or result in death or hospitalization might be considered serious when, based upon appropriate medical and scientific judgment, they might jeopardize the patient/subject or might require medical or surgical intervention

to prevent one of the other serious outcomes listed above);

- Any suspected transmission via a medicinal product of an infectious agent.

Grade is defined as the severity of the AE. The NCI Common Terminology Criteria for Adverse Events (CTCAE) Version – 4.0 will be used for grading. The following general criteria are used for grading.

- 0 – No adverse event or within normal limits
- 1 – Mild adverse event
- 2 – Moderate adverse event
- 3 – Severe adverse event
- 4 – Life-threatening or disabling adverse event
- 5 – Fatal adverse event

Attribution is defined as the determination of whether an adverse event is related to a medical treatment or procedure. Attribution categories are as follows:

- *Unrelated* The adverse event is *clearly NOT related* to therapy
- *Unlikely* The adverse event is *doubtfully related* to therapy
- *Possible* The adverse event *may be related* to therapy
- *Probable* The adverse event is *likely related* to therapy
- *Definite* The adverse event is *clearly related* to therapy

Suspected Adverse Reaction is defined as any adverse event for which there is a reasonable possibility that the drug caused the adverse event (21 CFR 312.23).

Unexpected Adverse Event is defined as an AE that is not consistent in nature or severity with the product information documented in the current Investigator's Brochure or package insert, or in the protocol, consent form, and/or prior reports.

Note: The following events are **not** identified as AEs in this study:

- Disease progression or relapse. However, clinical events associated with progression/relapse may be reportable as AEs.
- Medical or surgical procedures in and of themselves, including those that require hospitalization (e.g., surgery, endoscopy, biopsy procedures) are not considered AEs. However, an event or condition requiring such procedures may be an AE.
- Abnormal laboratory values will be identified and recorded as AEs only if clinical intervention is required as a result.

14.2 Adverse Event Monitoring

AEs of Grade 3 and above, and SAEs occurring at any grade will be monitored and recorded in study-specific case report forms (CRFs) from the time of study enrollment through 30 days following the end of study treatment or 100 days after the last dose of nivolumab whichever is later or until the patient receives an alternative anti-cancer therapy.. AEs related to lymph node (tumor) biopsies

that are done solely for research study screening purposes will be monitored, recorded, and reported according to the same standards, with the exception that assessment of study drug attribution will be excluded from reporting criteria.

The Sponsor-Investigator will assess AE grading, attribution, and expectedness.

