1.2.5. To correlate response with CD30 density as measured by flow cytometry

1.2.6. To evaluate the tolerability of the weekly regimen in patients previously exposed to brentuximab vedotin. To explore the tolerability of brentuximab vedotin and nivolumab in patients previously exposed to brentuximab vedotin in a 21-day cycle.

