8.4 Modifications for study treatment-related peripheral neuropathy

Note: these rules apply to **EVERY** dose of study drug and are relevant for treatment-emergent AEs only.

Table 1. Dose Modification Guidelines for Treatment-Related Peripheral Neuropathy

Toxicity	Grade 1	Grade 2	Grade 3 or Grade 4
Neuropathy: Motor	Continue at the same dose and schedule	Withhold dose until toxicity is Grade ≤ 1 or has returned to baseline. First occurrence: Reduce dose to 1.2mg/kg . Second occurrence: Omit Day 8 dosing from subsequent cycles. Third occurrence: patient will be removed from study.	Discontinue treatment at the discretion of the Sponsor-Investigator.
Neuropathy: Sensory	Continue at the same dose and schedule.	Withhold dose until toxicity is Grade ≤ 1 or has returned to baseline. First occurrence: Reduce dose to 1.2mg/kg . Second occurrence: Omit Day 8 dosing from subsequent cycles. Third occurrence: patient will be removed from study.	Discontinue treatment at the discretion of the Sponsor-Investigator.

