15.0 DATA AND SAFETY MONITORING PLAN

Ongoing trial oversight is carried out by the Principal Investigator and the study coordinator. These individuals will meet on a regular basis to review recently acquired data and adverse events. The data recorded within the research charts and protocol database is compared with the actual data that is available from the medical record and/or clinical histories. Data detailed in the research case report forms includes the nature and severity of all toxicities, which are also reported as described above.

Institutional support of trial monitoring is provided in accordance with the FHCC Institutional Data and Safety Monitoring Plan. Under the provisions of this plan, the FHCC Clinical Research Support office coordinates monitoring for data accuracy and compliance by consultants, contract research organizations, or FHCC employees unaffiliated with the conduct of the study. Independent monitoring visits occur at specified intervals determined by the assessed risk level of the study and the findings of previous visits. In addition, protocols are reviewed at least annually by the Data and Safety Monitoring Committee (DSMC) and the Institutional Review Board (IRB). The DSMC reviews accrual, adverse events, stopping rules, and adherence to the data and safety monitoring plan for studies actively enrolling or treating patients. The

FHCC/Cancer Consortium IRB reviews the study progress and safety information to assess continued acceptability of the risk-benefit ratio for human subjects. Approval of both committees as applicable is necessary to continue the study.

This protocol does not require a separate data safety monitoring board. The trial will comply with the standard guidelines set forth by the regulatory committees of the FHCC (Scientific Review Committee, IRB, DSMC) and other state and federal guidelines.

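### AE recording starts at a higher grade than treatment changes do, conflicts with section 15.0, and has no scheduled check late in the 100-day nivolumab window

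*Combined protocol and SAP*

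**What the plan says.** **What is recorded.** Section 14.2 sets the rule: "AEs of Grade 3 and above, and SAEs occurring at any grade will be monitored and recorded in study-specific case report forms (CRFs"). Section 15.0 describes the forms differently: "Data detailed in the research case report forms includes the nature and severity of all toxicities".

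**Laboratory values.** Section 14.1 includes abnormal laboratory findings in its definition of an AE, then restricts them: "Abnormal laboratory values will be identified and recorded as AEs only if clinical intervention is required as a result". It does not say what counts as intervention.

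**How long.** Under 14.2, recording runs from enrolment "through 30 days following the end of study treatment or 100 days after the last dose of nivolumab whichever is later". It ends sooner for anyone who starts a different cancer treatment.

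**When AEs are looked for.** The calendar in section 11.0 marks AE assessment at pre-entry, before each cycle and post therapy. Footnote 7 times the last of these: "Post therapy studies should be done 3 - 5 weeks post cycle 4 or after the patient's last cycle, whichever comes first". The Follow-Up column marks only a physical examination, done per standard of care; footnote 8 gives three-monthly visits in the first year as typical.

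**What changes treatment.** For Grade 2 neuropathy, Table 1 in section 8.4 withholds the dose and then specifies "First occurrence: Reduce dose to 1.2mg/kg", with further steps up to removal at a third occurrence. Section 8.5.1 allows delay for clinically significant Grade 2 or 3 events. Sections 8.1 to 8.3 hold a cycle on blood counts, creatinine or liver tests.

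**What the data are for.** Objective 1.2.6, listed as exploratory, includes: "To explore the tolerability of brentuximab vedotin and nivolumab in patients previously exposed to brentuximab vedotin in a 21-day cycle".

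**The concern.** The grade at which an event must be recorded is higher than the grade at which treatment is altered. A patient could have brentuximab vedotin withheld, reduced and finally stopped for non-serious Grade 2 neuropathy without 14.2 requiring one AE entry. This matters in a population that has all had the drug before and that 5.2.7 allows to enter with Grade 1 neuropathy caused by it.

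Sections 14.2 and 15.0 also describe two different safety datasets. Staff working from one would collect different data from staff working from the other, and the bodies reviewing adverse events could not tell which they had.

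The recording window was set at 100 days after nivolumab, but the calendar stops asking about AEs well before that. Late events then reach the record only if someone happens to report or notice them.

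Each gap can only remove events, so any bias in the tolerability description is in the favourable direction.

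**Working it through.** The plan states no sample size, event count or precision for tolerability, so there is no figure to reproduce. The check compares the rules and counts days.

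**1. Recording rule against action rules (14.2 and 14.1 against section 8)**

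| Event | Effect on treatment | AE entry required under 14.2? |
|---|---|---|
| Non-serious Grade 2 neuropathy | Hold, then reduction, omission or removal (Table 1) | No |
| Other non-serious Grade 2 AE | Delay allowed (8.5.1) | No |
| Blood counts, creatinine or liver tests outside limits | Cycle delayed (8.1-8.3) | Unclear |
| Grade 3+ AE, or SAE of any grade | Various | Yes |

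The laboratory row passes two filters. Section 14.1 must first accept the value as an AE, which depends on whether a delay is intervention. Then 14.2 still requires Grade 3 or a serious event. A delay caused by a lower-grade, non-serious value therefore stays outside 14.2 even if delay is accepted as intervention.

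**2. Days without a scheduled AE assessment**

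Inputs: window of 100 days after the last nivolumab dose (14.2); post-therapy visit at 3-5 weeks, or 21-35 days (footnote 7); 21-day cycle (7.2). Assumption: the last nivolumab dose is on Day 1 of the last cycle, as in the Arm B schema.

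Formula: unscheduled days = 100 - day of the post-therapy visit.

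- Timed from the last dose: visit on day 21-35. 100 - 35 = 65 and 100 - 21 = 79, so **65-79 days**.
- Timed from the end of the last cycle: visit on day 21 + 21 = 42 to 21 + 35 = 56. 100 - 56 = 44 and 100 - 42 = 58, so **44-58 days**.

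These are maxima for patients who start no other therapy; for those who do, recording ends earlier.

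**3. Would the typical three-monthly visit fill the gap?**

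Take three months as 91 days. Counted from the last dose, the visit falls on day 91, inside the window. Counted from the end of the cycle, it falls on day 21 + 91 = 112. Counted from the post-therapy visit, it falls between 21 + 91 = 112 and 56 + 91 = 147. Only the first is in time, and no AE assessment is marked for it.

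**4. How many patients might the Grade 2 gap touch?**

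The documents give no Grade 2 neuropathy rate, so this step is an assumption shown as a range. With n = 20 in Arm B, expected count = 20p and P(at least one) = 1 - (1 - p)^20.

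| Assumed rate p | Expected patients | P(at least one) |
|---|---|---|
| 10% | 2 | 0.88 |
| 20% | 4 | 0.99 |
| 30% | 6 | >0.99 |
| 40% | 8 | >0.99 |

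Even at the low end, at least one such patient is likely.

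**The case against.** The strongest defence is proportionality. This is a pilot of up to 20 patients in Arm B. Section 1.2 says the exploratory objectives will be met as far as routine clinical data allow, and success in 13.1 is judged on response alone. A Grade 3 threshold is a defensible economy, and SAEs of any grade, including important medical events, are kept. That stands as a limit on the importance of the point. It does not explain why 14.2 and 15.0 disagree, or why events that end treatment may be left off the AE record.

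The defence also rules out several stronger readings that a reader might infer:

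- *That most of the nivolumab window is not covered.* Section 14.2 requires recording throughout, and 14.3 requires related SAEs to be reported beyond 30 days after discontinuation. What is missing is a scheduled look. Footnote 7 refers to the cycle, which favours the 44-58 day count, and on that count the word most is borderline.
- *That Grade 2 neuropathy will never be captured.* Section 15.0 points the other way, the calendar's AE assessment has no grade floor, and Table 1 must be applied at every dose. Capture is ambiguous, and dose changes may be recoverable from medical records.
- *That untreated cytopenias will be lost, in about 4 of 20 patients (0.21 x 20 = 4.2).* Blood counts and chemistry are scheduled before each cycle and post therapy, section 16.0 provides for keeping laboratory data, and those values can be graded later. The 21% in section 2.3 comes from studies of brentuximab vedotin alone, one of which gave up to 16 cycles. It does not carry over to up to four cycles of the combination.
- *That unrecorded infusion reactions drive dose changes.* Sections 7.4 and 7.5 attach only additional premedication to Grade 1-2 reactions.

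**Conclusion.** The concern holds as a contradiction plus two gaps in ascertainment, and it should be corrected. Sections 14.2 and 15.0 cannot both describe the forms. Under 14.2, non-serious Grade 2 events that change treatment need no AE entry, and laboratory-driven delays may go unrecorded. After the post-therapy visit, capture is passive for 65-79 of the 100 days if timed from the last dose, or 44-58 if timed from the end of the cycle.

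Toxicity is therefore likely to be understated for objective 1.2.6 and for the acceptable-safety part of the hypothesis in section 2.8. By how much cannot be computed from the documents; the 2 to 8 patients shown above rest wholly on assumed rates. It would go too far to say that tolerability cannot be assessed or will certainly look better than it is, because Grade 3+ events and SAEs are still required and source records may supply part of the rest. The primary response rate is unaffected.

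The day counts assume that the last nivolumab dose opens the last cycle and that no other anti-cancer therapy has begun.

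**What to change.** The change concerns data capture only; no dose or clinical rule is altered.

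- **14.2:** also record AEs of any grade that lead to a hold, reduction, delay or removal, and peripheral neuropathy of any grade with its baseline grade.
- **14.1 and 14.2:** record Grade 3+ abnormalities from scheduled laboratory tests whether or not treated, and state that a treatment delay counts as intervention.
- **11.0:** mark one AE check in the Follow-Up column, by chart review or telephone, at about day 100 after the last nivolumab dose unless alternative therapy has started. State whether the 3-5 weeks in footnote 7 run from the last dose or from the end of the cycle.
- **15.0:** reword so that it describes the same dataset as 14.2.

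Cost: a few more form entries for up to 20 patients over at most 4 cycles, mostly from visits and tests already scheduled, plus one contact per patient. The toxicity table may look less favourable. Arm A is closed, so the change acts on Arm B.
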